16.4 Quality Assurance

In accordance with the FDA regulations^{75,76,77,86} the EU Clinical Trials Directive⁷⁸, the ICH Harmonised Guideline: Integrated Addendum to ICH E6(R1): Guideline for GCP E6(R2),⁷⁴ and the sponsor's audit plans, representatives from GW's Clinical Quality Assurance Department may select this trial for audit. Inspection of center facilities, e.g. pharmacy, drug storage areas, and laboratories and review of trial-related records will occur to evaluate the trial conduct and compliance with the protocol, the EU Clinical Trials Directive,⁷⁸ the ICH Harmonised Guideline: Integrated Addendum to ICH E6(R1): Guideline for GCP E6(R2),⁷⁴ and applicable regulatory requirements.

16.5 Compensation

GW will indemnify the investigator and the trial center in the event of any claim in respect of personal injury arising due to a patient's involvement in the trial, provided that the trial protocol has been adhered to. This would include claims arising out of or relating to the administration of the IMP or any clinical intervention or procedure

Study Code: GWND19002
EudraCT Number: 2019-001605-24
Clinical Protocol V2 18Dec19

provided for or required by the protocol to which the clinical trial patient would not otherwise have been exposed, provided that there is no evidence of negligence on behalf of the investigator or their team. GW will not be liable for any claims arising from negligence on the part of the investigator or their team.

16.6 Publication Policy

GW recognizes that there is a responsibility under the regulatory guidelines to ensure that results of scientific interest arising from this clinical trial are appropriately published and disseminated. They will coordinate this dissemination and may solicit input and assistance from the chief/principal investigators. A summary of the results of this trial will be made available on <http://www.clinicaltrials.gov> and <http://www.clinicaltrialsregister.eu/> (as applicable), as required by US and EU Law.

The raw data from this trial may be obtained by the PIs or by their steering committee representatives on request. Should they wish, PIs are allowed to conduct their own analyses and are permitted to present such information along with methods and results of the clinical trial at symposia or national or regional professional meetings and to publish it in theses or dissertations.

All publications, e.g. manuscripts, abstracts, oral/slide presentations, or book chapters based on this trial, must be submitted to the GW Medical Writing Department and, as applicable, GW Publication Committee for corporate review before release. To ensure adequate time for GW to make comments and suggestions where pertinent, all such material should be submitted to them at least 60 days prior to the date for submission for publication, public dissemination, or review by a publication committee. The PIs must then incorporate all reasonable comments made by GW into the publication.

GW also reserves the right to delay the submission of such information by a period of up to 6 months from the date of first submission to them in order to allow for steps to protect proprietary information where applicable.

16.7 Intellectual Property Rights

All intellectual property rights owned by or licensed to either GW or the PIs, other than those arising from the clinical trial, will remain their property. All intellectual property rights arising out of the clinical trial will vest in or be exclusively licensed to GW, and as such, the PI must promptly disclose all knowledge to GW and refrain from using such knowledge without the prior written consent of GW.

Study Code: GWND19002
EudraCT Number: 2019-001605-24
Clinical Protocol V2 18Dec19

16.8 Confidential Information

GW and the PI must ensure that only personnel directly concerned with the trial have access to confidential information and that any information coming to either party about the other during the course of the trial must be kept strictly confidential and must not be disclosed to any third party or made use of without the prior written consent of the other.

Study Code: GWND19002
 EudraCT Number: 2019-001605-24
 Clinical Protocol V2 18Dec19

Appendix 1 Schedule of Assessments

Visit Number	1	2 ^a	3 ^a	4	5	6	7	8	9	10	11	12	13	14 ^{b,c} EoT/ Withdrawal	15 (end of taper)	16 ^a (follow- up)
Day Number (Visit Window)	1	8 (±3)	15 (± 3)	29 (± 7)	57 (± 7)	85 (± 7)	141 (± 7)	197 (± 7)	281 (± 7)	365 (± 7)	456 (± 7)	547 (± 7)	638 (± 7)	729 (± 7)	739 (+ 7)	767 (+ 7)
Informed consent and assent ^d	X ^e															
Eligibility check	X ^e															
Concomitant medications		X	X	X	X	X	X	X	X	X	X	X	X	X	X	X
New medical history	X ^e															
Adverse events	X ^e	X	X	X	X	X	X	X	X	X	X	X	X	X	X	X
Menstruation question (where appropriate)								X		X				X		
Physical examination (including body weight)	X ^f			X		X		X	X	X		X		X	(X)	
Height								X		X		X		X		
ECG	X ^f			X		X		X		X		X		X	(X)	
Vital signs	X ^g			X	X	X	X	X	X	X		X		X	X	
Clinical laboratory blood sampling (hematology and biochemistry) ^h	X ^f			X	X	X		X	X	X		X		X	(X)	
Hepatic function monitoring panel ⁱ							X ⁱ				X ⁱ		X ⁱ			
Dipstick urinalysis (where possible)	X ^f							X		X		X		X	(X)	

Study Code: GWND19002
 EudraCT Number: 2019-001605-24
 Clinical Protocol V2 18Dec19

Visit Number	1	2 ^a	3 ^a	4	5	6	7	8	9	10	11	12	13	14 ^{b,c} EoT/ Withdrawal	15 (end of taper)	16 ^a (follow- up)
Day Number (Visit Window)	1	8 (±3)	15 (±3)	29 (±7)	57 (±7)	85 (±7)	141 (±7)	197 (±7)	281 (±7)	365 (±7)	456 (±7)	547 (±7)	638 (±7)	729 (±7)	739 (+7)	767 (+7)
Serum pregnancy test (if appropriate)								X		X		X		X		
Caregiver completed questionnaire/assessment	RSBQ			X	X	X	X	X		X				X		
	CSHQ					X		X		X				X		
	Caregiver QoL questionnaire (SF-36)							X		X				X		
	Patient QoL questionnaire (CHQ-PF50)							X		X				X		
	Hospital Services Use Questionnaire	X ^g			X	X	X	X	X		X			X		
	Tanner Staging (where appropriate)							X		X				X		
	Caregiver Assessment of Rett Symptoms				X	X	X	X	X		X			X		
MBA-9						X		X		X			X			
CGI-S				X	X	X	X	X		X			X			
CGI-I				X	X	X	X	X		X			X			
Suicidality assessment	X ^g			X	X	X	X	X	X	X		X		X	X	
GWP42003-P dispensing	X ^e			X	X	X	X	X	X	X	X	X	X	X		
GWP42003-P collection and compliance review				X	X	X	X	X	X	X	X	X	X	X	X	
Dosing schedule ^j	X	X	X	X	X	X	X	X	X	X	X	X	X	X		

Study Code: GWND19002

EudraCT Number: 2019-001605-24

Clinical Protocol V2 18Dec19

(X) = if clinically indicated; EoT = end of treatment

a Visit to be conducted by telephone.

b To be performed to all patients completing or withdrawing from the trial. Patients who withdraw early should commence the 10-day GWP42003-P taper period, if possible.

c A safety follow-up Visit 4 weeks after last GWP42003-P dose is required for all patients who withdraw from the trial or complete the trial.

d Informed consent must be obtained prior to any trial-related procedures. In cases where the patient possesses adequate understanding, assent will be taken along with parent(s)/legal representative consent. The nominated caregiver will be asked to complete the quality of life questionnaires.

e Always required.

f Required only if OLE Visit 1 is > 28 days after RCT Visit 9.

g Required if OLE Visit 1 does not occur on the same day as RCT Visit 9.

h Determination of serum IGF-1 levels at Visits 1, 8, 10, and 14 only; IGF-1 laboratory results will remain blinded throughout the trial.

i Hepatic function monitoring is required following increases in GWP42003-P dose or introduction of medications that are known to impact liver function. If the concerned change does not occur within 1 month of a scheduled biochemistry assessment, the investigator should perform an additional hepatic monitoring within 1 month of the change. Hepatic monitoring at Visit 7, 11 and 13 is required for patients taking concomitant valproic acid or whose dose exceeds 15 mg/kg/day.

j The dosing schedule is to be completed by the caregiver daily throughout the trial and reviewed at Visits 2 through 15.

Study Code: GWND19002
EudraCT Number: 2019-001605-24
Clinical Protocol V2 18Dec19

Enrolled participant	Any patient whose parent(s)/legal representative has provided written informed consent for the patient to take part in the trial and, if possessing adequate understanding to do so, who has provided informed assent.
International normalized ratio	A calculation made to standardize prothrombin time.
Investigational medicinal product	Term used to describe both investigational active product and reference therapy (placebo).
Investigator	Trial principal investigator or a formally delegated study physician.

1 RATIONALE

This addendum covers protocol changes which are applicable to patients who were affected by COVID-19 pandemic containment measures during their participation in the parent study GWND18064:

- Allowance for patients to enroll into GWND19002 after the point of GWND18064 follow-up (Visit 11).
- Allowance for patients who withdrew from GWND18064 due to COVID-19 pandemic containment measures to enroll into GWND19002 at a later date, when appropriate.

There are no implications for the conduct of the GWND19002 trial for patients that were not affected by the COVID-19 pandemic containment measures, and no changes are required to the Clinical Protocol currently approved at each territory. Please see [Section 3](#) for full details of changes.

2 SUMMARY OF THE ANNEX

2.1 Objective

Due to the COVID-19 pandemic situation, patients may have been unable to attend the scheduled clinic visits or local safety assessments deemed required for the safe continuation of investigational medicinal product (IMP) dosing. This situation may have resulted in the inability to complete GWND18064 or enroll into GWND19002 within the timeline stipulated in the protocol (up to GWND18064 Visit 11).

The objective of this annex is to define when patients whose participation in Study GWND18064 was disrupted by COVID-19 pandemic containment measures are allowed to take part in GWND19002 despite not meeting the criterion ‘Patient has completed all scheduled visits of the treatment phase of the randomized controlled trial (RCT), GWND18064, and has transitioned to open-label extension (OLE) by the point of RCT follow-up (Visit 11)’ defined in the GWND19002 protocol. The measures implemented via this protocol annex do not affect the primary objective of GWND19002, which is to evaluate the long-term safety of GWP42003-P in patients with Rett Syndrome.

3 DESIGN AND PROCEDURES

3.1 Patient Eligibility

With the exception of the inclusion criterion that requires patients must have completed all scheduled visits of the treatment phase of the RCT, GWND18064, and transitioned to OLE by the point of RCT follow-up (Visit 11), all inclusion and exclusion criteria defined in the GWND19002 protocol must be met. In addition, the following inclusion criteria apply:

Inclusion criteria

- Patient has completed all scheduled visits of the treatment phase of the RCT, either in clinic or completed as many scheduled assessments as feasible remotely, or has withdrawn from GWND18064 after discussion with the medical monitor due to inability to adequately monitor safety and benefit risk.
- Visit 1 is taking place no later than 3 months after screening of new subjects for study GWND18064 has reopened at their trial site.

Exclusion criteria

- Any history of suicidal behavior or any suicidal ideation in the last month or at Visit 1.
- Patient has clinically relevant abnormalities in the electrocardiogram measured at Visit 1 (including QT interval, corrected by Bazett's correction formula [QTcB] > 450 msec, average of 3 measurements).
- Patient has any known or suspected hypersensitivity to cannabinoids or any of the excipients of the IMP (active and placebo), such as sesame oil.
- Patient has moderately impaired hepatic function at screening, defined as serum ALT or AST > 3 × ULN **or** total bilirubin [TBL] > 2 × ULN.

This criterion can only be confirmed once the Visit 1 laboratory results are available. If Visit 1 laboratory results indicate the patient is not eligible, the patient must be withdrawn. Prior to withdrawal for the transaminase elevations noted above, the investigator may choose to confirm the transaminase elevations by repeating the following laboratory tests within 24 to 48 hours: ALT, AST, TBL, international normalized ratio, % eosinophils, gamma-glutamyl transferase, alkaline phosphatase, and eosinophils. Should the above transaminase elevation criteria be confirmed, the patient must be withdrawn from the trial.

- Patient has received an IMP (other than GWND18064 IMP) since participation in GWND18064.
- Patient has been taking felbamate for less than 1 year prior to Visit 1

- Patient is currently using or has used recreational or medicinal cannabis, cannabinoid-based medications (including Sativex[®] [nabiximols]) or cannabidiol oral solutions (excluding GWND18064 IMP) within the 3 months prior to Visit 1 and is unwilling to abstain for the duration of the trial.
- Patient has any other systemic dysfunction (e.g., gastrointestinal, renal, respiratory) or significant disease or disorder which, in the opinion of the investigator, may either put the patient at risk because of participation in the trial, may influence the result of the trial, or the patient's ability to participate in the trial.
- Any abnormalities identified following a physical examination of the patient that, in the opinion of the investigator, would jeopardize the safety of the patient if the patient took part in the trial.
- Female patient is pregnant (positive pregnancy test) or lactating.

3.2 Trial Procedures

3.2.1 Visit 1 Procedures

Visit 1 must include the Visit 1 assessments listed in the GWND19002 protocol as required for patients for whom OLE Visit 1 occurs > 28 days after RCT Visit 9.

In addition the following assessments are required:

- Concomitant medications review (details of all current and recent medication; i.e., those taken within the previous 14 days of Visit 1)
- Menstruation question (where appropriate)
- Height
- Serum pregnancy test (if appropriate)
- Rett Syndrome Behaviour Questionnaire
- Children's Sleep Habits Questionnaire
- Caregiver QoL questionnaire (SF-36)
- Patient QoL questionnaire (CHQ-PF50)
- Tanner Staging (where appropriate)
- Caregiver Assessment of Rett Symptoms
- 9-items Motor Behavioral Assessment
- Clinical Global Impressions - Severity
- Clinical Global Impressions - Improvement (completed in relation to the baseline of the RCT, GWND18064 Visit 2)

4 DATA ANALYSIS

All Visit 1 data will be summarized for patients enrolling in the OLE under this protocol annex. Their data will be summarized in the same way as that of patients enrolling in the OLE under the GWND19002 protocol. The summary tables will present data from patients enrolling in the OLE under this protocol annex combined with that of patients enrolling in the OLE under the GWND19002 protocol. Their data will also be presented separately.

5 IMPLEMENTATION OF THE ANNEX

This clinical protocol annex will be issued in conjunction with the current version of the main clinical trial protocol to country/sites affected by the COVID-19 pandemic containment situation. It will be kept in the trial master file at GW as well as in each investigational centre file and, if applicable, pharmacy site file.

1 RATIONALE

This annex covers protocol changes which are applicable to patients who were affected by COVID-19 pandemic containment measures during their participation in the parent study GWND18064 or withdrew from GWND18064 due to sponsor administrative decision:

- Allowance for patients to enroll into GWND19002 after the point of GWND18064 follow-up (Visit 11).
- Allowance for patients who withdrew from GWND18064 due to COVID-19 pandemic containment measures or withdrew from GWND18064 due to sponsor administrative decision to enroll into GWND19002 at a later date, when appropriate.

There are no implications for the conduct of the GWND19002 trial for patients who were not affected by the COVID-19 pandemic containment measures or administrative withdrawal, and no changes are required to the Clinical Protocol currently approved at each territory. Please see [Section 3](#) for full details of changes.

2 SUMMARY OF THE ANNEX

2.1 Objective

Due to the COVID-19 pandemic situation, patients may have been unable to attend the scheduled clinic visits or local safety assessments deemed required for the safe continuation of investigational medicinal product (IMP) dosing. This situation may have resulted in the inability to complete GWND18064 or enroll into GWND19002 within the timeline stipulated in the protocol (up to GWND18064 Visit 11).

The objective of this annex is to define when patients whose participation in Study GWND18064 was disrupted by COVID-19 pandemic containment measures are allowed to take part in GWND19002 despite not meeting the criterion ‘Patient has completed all scheduled visits of the treatment phase of the randomized controlled trial (RCT), GWND18064, and has transitioned to open-label extension (OLE) by the point of RCT follow-up (Visit 11)’ defined in the GWND19002 protocol. This annex also applies to patients who withdrew from GWND18064 due to sponsor administrative decision. The measures implemented via this protocol annex do not affect the primary objective of GWND19002, which is to evaluate the long-term safety of GWP42003-P in patients with Rett Syndrome.

3 DESIGN AND PROCEDURES

3.1 Patient Eligibility

With the exception of the inclusion criterion that requires patients must have completed all scheduled visits of the treatment phase of the RCT, GWND18064, and transitioned to OLE by the point of RCT follow-up (Visit 11), all inclusion and exclusion criteria defined in the GWND19002 protocol must be met.

In addition, the following inclusion criteria apply:

Inclusion criteria

- Patient has completed all scheduled visits of the treatment phase of the RCT, either in clinic or completed as many scheduled assessments as feasible remotely, or has withdrawn from GWND18064 after discussion with the medical monitor due to inability to adequately monitor safety and benefit risk, or has withdrawn from GWND18064 due to sponsor administrative decision.

For patients who enroll after the point of RCT follow-up (Visit 11) the following additional exclusion criteria must be confirmed:

Exclusion criteria

- Any history of suicidal behavior or any suicidal ideation in the last month or at Visit 1.
- Patient has clinically relevant abnormalities in the electrocardiogram measured at Visit 1 (including QT interval, corrected by Bazett's correction formula [QTcB] > 450 msec, average of 3 measurements).
- Patient has any known or suspected hypersensitivity to cannabinoids or any of the excipients of the IMP (active and placebo), such as sesame oil.
- Patient has moderately impaired hepatic function at screening, defined as serum ALT or AST > 3 × ULN **or** total bilirubin [TBL] > 2 × ULN.
This criterion can only be confirmed once the Visit 1 laboratory results are available. If Visit 1 laboratory results indicate the patient is not eligible, the patient must be withdrawn. Prior to withdrawal for the transaminase elevations noted above, the investigator may choose to confirm the transaminase elevations by repeating the following laboratory tests within 24 to 48 hours: ALT, AST, TBL, international normalized ratio, % eosinophils, gamma-glutamyl transferase, alkaline phosphatase, and eosinophils. Should the above transaminase elevation criteria be confirmed, the patient must be withdrawn from the trial.
- Patient has received an IMP (other than GWND18064 IMP) since participation in GWND18064.

- Patient has been taking felbamate for less than 1 year prior to Visit 1
- Patient is currently using or has used recreational or medicinal cannabis, cannabinoid-based medications (including Sativex® [nabiximols]) or cannabidiol oral solutions (excluding GWND18064 IMP) within the 3 months prior to Visit 1 and is unwilling to abstain for the duration of the trial.
- Patient has any other systemic dysfunction (e.g., gastrointestinal, renal, respiratory) or significant disease or disorder which, in the opinion of the investigator, may either put the patient at risk because of participation in the trial, may influence the result of the trial, or the patient's ability to participate in the trial.
- Any abnormalities identified following a physical examination of the patient that, in the opinion of the investigator, would jeopardize the safety of the patient if the patient took part in the trial.
- Female patient is pregnant (positive pregnancy test) or lactating.

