3.2.2 Clinical Studies

Human efficacy data from 3 positive Phase 3 trials in patients (predominantly pediatric patients) with treatment-resistant epilepsies support a role for GWP42003-P as a treatment for central nervous system disorders. Overall, GWP42003-P was generally well tolerated at doses up to 20 mg/kg/day; adverse events (AEs) were usually mild to moderate in severity and transient. Elevated liver enzymes (particularly transaminases alanine aminotransferase [ALT] and aspartate aminotransferase [AST], and less commonly reported terms of abnormal liver function tests and hepatotoxicity) have been reported in some patients receiving GWP42003-P for severe, refractory epilepsies, notably in patients taking concomitant valproic acid. None of the cases fulfilled the Hy's Law criteria for potential severe liver injury. There were no cases with a concomitant increase in bilirubin $> 2 \times$ upper limit of normal (ULN). Monitoring of the blood levels of enzymes that are markers of liver function is advised, particularly at the start of treatment and with dose increases of GWP42003-P, as well as at the time of initiation or dose increase of concomitant medication.

Study Code: GWND19002
EudraCT Number: 2019-001605-24
Clinical Protocol V2 18Dec19

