9.1.1 Clinic Visits

9.1.1.1 Visit 1 (Day 1)

Every effort should be made for this visit to take place on the same day as the RCT ‘End of Treatment’ visit. However, patients can still enter the OLE trial up to the point of the RCT follow-up (Visit 11).

OLE Visit 1 Assessments required for all patients:

- Informed consent and assent
- Eligibility check
- New medical history
- AE review
- GWP42003-P dispensing

OLE Visit 1 assessments required if OLE Visit 1 occurs on a different date than RCT Visit 9:

- Vital signs
- Hospital Services Use Questionnaire
- Suicidality assessment

OLE Visit 1 assessments required if OLE Visit 1 occurs > 28 days after RCT Visit 9:

- Physical examination (including weight)
- ECG
- Clinical laboratory blood sampling (hematology and biochemistry)
- Dipstick urinalysis (where possible)

Patients who satisfy all of the inclusion criteria and none of the exclusion criteria specified in [Section 6](#) will begin the treatment period.

Patients will be dispensed sufficient GWP42003-P and a dosing schedule for the following 3 weeks. Caregivers will be instructed on how to use the dosing schedule and how to measure and administer the medication. At the next visit, all GWP42003-P (used and unused) will be collected, and a check of the returned GWP42003-P against usage should be made.

Study Code: GWND19002

EudraCT Number: 2019-001605-24

Clinical Protocol V2 18Dec19

Based on [Section 9.1.3](#), assessments may be performed at unscheduled visits in the event of a safety concern, as deemed necessary by the investigator.

The investigator should review the laboratory results as soon as these become available.

If the results show a patient is ineligible, the patient will fail screening.

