3.2 Trial Procedures

3.2.1 Visit 1 Procedures

For patients who enroll after the point of RCT Visit 11, GWND19002 Visit 1 must include the Visit 1 assessments listed in the GWND19002 protocol as required for patients for whom OLE Visit 1 occurs > 28 days after RCT Visit 9 and, in addition, the following assessments are required:

- Concomitant medications review (details of all current and recent medication; i.e., those taken within the previous 14 days of Visit 1)
- Menstruation question (where appropriate)
- Height
- Serum pregnancy test (if appropriate)
- Rett Syndrome Behaviour Questionnaire
- Children's Sleep Habits Questionnaire
- Caregiver QoL questionnaire (SF-36)
- Patient QoL questionnaire (CHQ-PF50)
- Tanner Staging (where appropriate)
- Caregiver Assessment of Rett Symptoms
- 9-items Motor Behavioral Assessment
- Clinical Global Impressions - Severity
- Clinical Global Impressions - Improvement (completed in relation to the baseline of the RCT, GWND18064 Visit 2)

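### Annex 1 V2 lets a patient whose remote RCT Visit 9 lacked labs, ECG or weight start OLE dosing within 28 days without them, because the Visit 1 re-test rules count from visit dates

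*Protocol*

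**What the plan says.** **Who may enter.** Annex 1 V2, Section 3.1, accepts patients who attended the RCT treatment visits in clinic or "completed as many scheduled assessments as feasible remotely". It names no minimum set of tests. It also accepts two groups of withdrawn patients.

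**What they must have at OLE Visit 1.** Two rules decide this.

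- Protocol V2, Section 9.1.1.1, lists examination with weight, ECG, bloods and dipstick under "OLE Visit 1 assessments required if OLE Visit 1 occurs > 28 days after RCT Visit 9". Footnote f of Appendix 1 puts it restrictively: "Required only if OLE Visit 1 is > 28 days after RCT Visit 9". SAP Table 1, footnote f, repeats this and adds only annex enrolment after RCT Visit 11.
- Annex 1 V2 uses the Visit 11 point. Section 3.1 introduces its extra exclusions (including Visit 1 ECG and liver values) with "For patients who enroll after the point of RCT follow-up (Visit 11) the following additional exclusion criteria must be confirmed". Section 3.2.1 opens: "For patients who enroll after the point of RCT Visit 11, GWND19002 Visit 1 must include the Visit 1 assessments".

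**What happens next.** Visits 2 and 3 are telephone calls (Section 9.1.2.1). Visit 4, on Day 29 ± 7, has unconditional examination, weight, ECG, hematology and biochemistry (Section 9.1.1.2).

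**The concern.** The 28-day waiver makes sense because RCT Visit 9 normally supplies results that are at most 28 days old. The annex admits patients for whom that may not be true, yet it leaves the waiver keyed to the date of the visit. A remote Visit 9 with no blood sample starts the 28-day clock just as a full clinic visit does.

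At stake is starting a drug with a known transaminase signal without a current liver panel or ECG, and setting weight-based volumes (Section 8.1.2) without a current weight. The protocol's own Section 3.2.2 says that liver-enzyme monitoring "is advised, particularly at the start of treatment and with dose increases of GWP42003-P". Former placebo patients also enter the extension (SAP Table 2), and for them OLE Day 1 is the first exposure. The sponsor thought Visit 1 liver values and QTcB important enough to exclude later annex entrants on them. An early entrant with no result is not screened in that way.

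**Working it through.** The plan has no figure to reproduce here. The check is a trace of the rules followed by day arithmetic, with Visit 1 as Day 1.

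**1. Which route requires tests at Visit 1**

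| Entry | Rule met | Labs, ECG, weight at Visit 1 |
|---|---|---|
| After the RCT Visit 11 point | Annex 3.1 and 3.2.1 | Required, with the annex exclusions |
| More than 28 days after RCT Visit 9, before Visit 11 | Protocol 9.1.1.1 | Required |
| 0–28 days after RCT Visit 9, test done there | None | Waived; result at most 28 days old |
| 0–28 days after RCT Visit 9, test not done there | None | Waived; no result from that visit |

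The last row is the gap. It needs Visit 1 to precede RCT Visit 11. The day of Visit 11 is not given. However, entry under the main protocol closes at Visit 11, so the 28-day rule has a use only if Visit 11 can fall more than 28 days after Visit 9.

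**2. What Visit 1 still requires in that row.** Consent or assent, eligibility check, new medical history, AE review and dispensing. Vital signs, the suicidality assessment and the hospital-use questionnaire are added if the date differs from RCT Visit 9. Labs, ECG and weight are not on either list.

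**3. First mandatory set.** Visit 4 is Day 29 ± 7, so Day 22 to Day 36, which is 22 − 1 = 21 to 36 − 1 = 35 days after the first OLE dose.

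**4. Dose permitted by then (Section 8.1.2).** 5 mg/kg/day from Day 1, 10 from Day 8 and 15 from Day 15. Time at 15 mg/kg/day before Visit 4: 22 − 15 = 7 to 36 − 15 = 21 days, 14 at the nominal day.

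**5. Interval between results**

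- Tested at RCT Visit 9: 0 + 21 = 21 to 28 + 35 = 63 days.
- Not tested there: 21 + g to 63 + g days, where g is the time from the last actual test back from RCT Visit 9.

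The documents do not give g. If a local test was done close to Visit 9, g is near 0 and there is no gap for that test. For scale only, assumed values of g = 28, 56 or 84 days give 49–91, 77–119 or 105–147 days.

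**6. Whether another rule forces an earlier test**

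- The opening paragraph of Section 6.2 and criteria 6.2.1 and 6.2.2 act on findings already in hand.
- Section 9.1.1.1 tells the investigator to review Visit 1 laboratory results when they arrive. It does not order them.
- Unscheduled assessments (Section 9.1.3) are optional.
- Hepatic monitoring is due within 1 month of a dose increase (Section 8.1.2). After a Day 8 step, the latest Visit 4 falls 36 − 8 = 28 days later, so Visit 4 satisfies it.

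None of these mandates a test before the first dose.

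**The case against.** The best reply is that this patient may not exist. Annex Section 2.1 describes patients "unable to attend the scheduled clinic visits or local safety assessments deemed required for the safe continuation of investigational medicinal product (IMP) dosing" and gives the consequence as not completing the RCT or entering late. That links missing safety tests to withdrawal or delay more than to prompt entry. The RCT protocol and its COVID measures are not supplied and may have required local tests at a remote Visit 9. Section 9.2.2 expects a serum pregnancy test at RCT Visit 9, negative for eligibility, in patients of childbearing potential, so a blood draw near that date is expected for them. An investigator with no liver result has good reason to obtain one, and dispensing details sit in a pharmacy manual that was not available. All of this stands as a limit on size. None of it changes the rule: the wording followed literally waives the test, and the annex sets no floor on what a remote visit must include.

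The other side is also right on two attributions that a reader might make.

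- The 21–35 days to first labs and the 7–21 days at 15 mg/kg/day are not caused by this gap. They apply to every early entrant. The specific increment is g.
- A missing OLE baseline is not specific to this patient. SAP 6.1.2 defines that baseline as the Visit 1 value, and no entrant within 28 days is required to have Visit 1 labs, ECG or weight. For repeated laboratory samples, SAP 9.2.1 speaks of the last value before OLE Visit 1, so an earlier RCT value might serve. Comparisons with the RCT baseline are untouched.

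**Conclusion.** The concern holds in a narrow form. For an annex patient who enters within 28 days of a remote RCT Visit 9 and before the Visit 11 point, a test missed at that visit is not required until Visit 4. Not required does not mean prohibited, since an investigator may still order it.

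The number of such patients is unknown and may be zero. The conclusion assumes that RCT Visit 11 had not yet been reached and that no RCT rule outside these documents supplied the test.

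Two broader readings are tempting but unsupported. One is that annex patients in general start untested: those entering after the Visit 11 point get the full set, and those more than 28 days after Visit 9 get labs, ECG and weight. The other is that patients withdrawn before RCT Visit 9 escape testing. The annex allows withdrawn patients "to enroll into GWND19002 at a later date, when appropriate", and those entering after the Visit 11 point are covered. For anyone without a Visit 9 date the trigger is undefined rather than waived, and the RCT protocol may define it.

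This is a cheap safety improvement worth making. It is not evidence that any patient was harmed or that the primary analysis fails.

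**What to change.** In Annex 1 V2, Section 3.2.1, and in footnote f as it applies to annex patients, key the rule to the test: *Hematology and biochemistry, ECG, and physical examination with weight are each required at OLE Visit 1 if that assessment was not actually obtained in the previous 28 days, whatever the date of RCT Visit 9 or 11.* In Section 3.1, apply the annex hepatic exclusion (ALT or AST > 3 × ULN, or total bilirubin > 2 × ULN) to the patients tested under this rule.

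The cost is one sentence plus a blood draw, ECG and weight for a few patients at a visit where the first dose is already taken in clinic (Section 13.6.1). Dosing need not wait, because the annex already lets the hepatic criterion be confirmed when Visit 1 results arrive. Weight is known the same day, and the central ECG report comes within 24 hours (Section 9.2.7). If labs return within 7 days (an assumption, as turnaround is not stated), they are known before the first permitted dose step on Day 8. The superseded Annex Version 1 asked for these tests from every annex patient, which shows only that the requirement is workable.
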